**NCT06027593**

**Background:**

Antibiotic resistance (AR) is increasing at an alarming rate, leading to substantial morbidity and mortality for patients with infections due to resistant bacteria. Antibiotic use, the main driver of antibiotic resistance, is common in clinical practice in both inpatient and outpatient settings. More than half of all adult and pediatric patients receive antibiotics during an inpatient stay. In the outpatient setting, the equivalent of 849 courses of antibiotics are prescribed for every 1,000 persons. However, up to 50% of these prescriptions are inappropriate.

Antibiotic stewardship (AS) has been shown to improve patient outcomes, decrease adverse events, and decrease antibiotic resistance. Tracking antibiotic use is a fundamental component of AS. Although strategies to track antibiotic use in meaningful ways have been attempted, these metrics typically track aggregate antibiotic use and are at best surrogate markers of inappropriate antibiotic use. Further, minimal research has evaluated the relationship between aggregate antibiotic use measures and inappropriate antibiotic prescribing. Because aggregate antibiotic use metrics don't necessarily measure inappropriate antibiotic use, antibiotic stewardship programs (ASPs) must utilize time-intensive strategies reliant on manual electronic health record (EHR) review, such as medication use evaluations, in order to qualitatively assess the appropriateness of antibiotic use. Ultimately, these limitations make current metrics less meaningful to clinicians and actionable by ASPs.

The increasing availability of EHRs across healthcare settings provides a unique opportunity to extract more data elements than ever before from the level of individual patients to the level of healthcare facilities. Utilizing these data elements has the potential to create more actionable metrics using individual indicators or groups of indicators to better identify infectious disease diagnoses and measure inappropriate antibiotic use for these conditions. In order to utilize EHR data in this way, performance characteristics of candidate indicators need to be systematically evaluated and then integrated into software that allows ASPs to perform these analyses on an ongoing basis.

In a prior research project conducted at Children's Hospital of Philadelphia (CHOP) and Penn (SHEPheRD Contract #200-2016-91796, titled "Assessing Appropriate Antibiotic Use in Hospitals and Outpatient Settings Through Electronic Health Records"), our research group developed several electronic indicators measuring appropriate antibiotic use for community acquired pneumonia (CAP) that were extractable using electronic data sources. These indicators measure two dimensions of antibiotic prescribing: 1) the choice of antibiotic agent and 2) the duration of antibiotic use.

The focus of the current protocol is to: 1) refine this electronic definition of CAP and the electronic indicators for appropriate antibiotic prescribing through a detailed chart review and validation process; 2) assess the impact of generating reports reflecting these indicators on the appropriateness of antibiotic use; and 3) to evaluate the acceptability and feasibility of delivering these reports to prescribers. If effective, these EHR-based approaches hold the promise to greatly enhance effectiveness and efficiency of AS initiatives.

As a secondary aim, we also seek to identify racial disparities in the appropriateness of antibiotic prescribing in patients hospitalized with CAP.

**Project Goals:**

The goals of this project are to:

- Aim 1: Refine the electronic definition of CAP and the electronic indicators for appropriate antibiotic prescribing through a detailed chart review and validation process
- Aim 2: Design and implement a scalable and sustainable AS feedback reported-based intervention for these populations informed by a rapid user-centered design process
- Aim 3: Track the impact of the stewardship intervention and report to key stakeholders (e.g., prescribers)

Secondary aim: To identify racial disparities in the appropriateness of antibiotic prescribing in patients hospitalized with CAP

**Study Design:**

Aim 1:

We will first conduct a retrospective descriptive study to refine and validate the previously developed electronic definition of CAP and indicators for appropriate antibiotic choice and duration.

To do this, we will first refine an electronic definition of CAP, which may include ICD-10 codes, antibiotic orders, and orders for radiographic studies suggesting a diagnosis of CAP. We will validate this definition through chart review to ensure that the electronic definition of CAP correctly identifies patients being for CAP based on documentation in the EHR. We will also evaluate the impact of various inclusion and exclusion criteria within the cohort, such as ICU admission and presence of chronic comorbid conditions (e.g., lung cancer, cardiopulmonary disease) on the sensitivity and specificity of this electronic definition of CAP.

As a secondary component of this aim, we will also compare this electronic definition of CAP with provider-selected indication. Upon ordering antibiotics for inpatients, providers must select the indication for the antibiotic; one of the possible indications is CAP. We will perform chart review on a subset of patients ordered for azithromycin or doxycycline within the first 48 hours of admission, given that these are common antibiotics ordered for CAP. Chart review to assess for provider intention to treat for CAP will serve as the gold standard. We will then compare the performance of the electronic definition and provider-selected indication with the chart review-based findings, assessing sensitivity and specificity of these two methods.

We will also validate our indicators of antibiotic appropriateness, which include appropriate antibiotic choice and duration. To validate these indicators, we will compare sensitivity and specificity of the electronic definition of appropriate antibiotic choice and duration compared to a “gold standard” of manual chart review. We will iterate these definitions until acceptable performance characteristics for the electronic indicators are achieved. These measures of appropriateness are based on national guidelines for appropriate antibiotic prescribing.

Finally, we will also collect data on prescribers, including the attending of record and clinicians placing orders, to evaluate whether the indicators for appropriate antibiotic choice and duration can be attributed to individual prescribers. Study measures for this aim will be purely descriptive.

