**Aim 2:**

We will then generate reports of appropriate antibiotic choice and duration using the indicators validated in Aim 1. Through a user-centered design process, we will optimize the structure and delivery of these feedback reports through conducting interviews with a small number of clinical provider stakeholders. We will also perform surveys of all clinicians during the intervention focused on feasibility and acceptability of the intervention.

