**Aim 3:**

We will conduct a quasi-experimental study in the adult inpatient settings measuring the impact of implementing the feedback reports on appropriateness of antibiotic choice and duration for CAP using the validated indicators. The baseline, pre-intervention period will last approximately up to 24 months and the intervention period will last up to 24 months.

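### Aim 1 accuracy figures: the indicators are tuned until they pass, with no later evaluation described, and charts from the CAP cohort give predictive value, not sensitivity or specificity of the CAP definition

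*Combined protocol and SAP*

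**What the plan says.** Project Goals and Study Design, Aim 1, set out to "refine and validate the previously developed electronic definition of CAP and indicators for appropriate antibiotic choice and duration". The CAP definition is still open at this stage. Its elements are listed as ones "which may include ICD-10 codes, antibiotic orders, and orders for radiographic studies suggesting a diagnosis of CAP", and it is to be refined and then validated by chart review. Candidate criteria such as ICU admission and comorbidity are to be judged within the cohort by their impact "on the sensitivity and specificity of this electronic definition of CAP".

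For the choice and duration indicators, manual chart review is the reference standard, and the rule for ending the work is: "We will iterate these definitions until acceptable performance characteristics for the electronic indicators are achieved". The next steps are Aim 2, which builds the feedback reports "using the indicators validated in Aim 1", and Aim 3, which measures "appropriateness of antibiotic choice and duration for CAP using the validated indicators".

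Study subjects defines the patient cohort by a pneumonia ICD-10 code, an antibiotic in the first 48 hours with conditions on its continuation, and chest imaging within 48 hours. It gives a different population, for the secondary component only: a random sample of adults given azithromycin or doxycycline within 48 hours. Those charts are for comparing the electronic definition with the provider-selected indication, "assessing sensitivity and specificity of these two methods".

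Outcomes names sensitivity and specificity of both the CAP definition and the indicators as the Aim 1 results. Sample size allows up to 1500 charts and does not divide them by task.

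**The concern.** There are two separate issues.

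**Selection for passing.** Stopping when performance looks good enough, and then reporting that same performance, selects results with favourable sampling error. Drawing a new batch for each revision does not remove this if the batch that passes is also the one reported.

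**Sampling frame.** Sensitivity needs CAP cases that the definition missed, and specificity needs non-CAP patients whom it correctly left out. A cohort assembled with the definition's own elements contains neither for the base definition.

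Readers will judge how well the feedback reports and the Aim 3 outcome classify encounters by these Aim 1 figures, so the figures should mean what their labels say.

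**Working it through.** The plan's one calculated sample size, 776, belongs to Aim 3 and is not in question. With two-sided 0.05, 80% power and equal periods (assumed, because the plan does not state them), n per period = [1.96·√(2·0.55·0.45) + 0.8416·√(0.25 + 0.24)]² / 0.10² = 387.3, so 388, or 776 in total. The figure of 1500 charts has no derivation to reproduce.

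**Inputs.** The documents give no chart numbers per task, number of revisions, target or expected accuracy. Everything in A to D is therefore assumed and shows size only. The calculations are for sensitivity; the same mechanism applies to specificity.

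**A. Best of several versions on the same charts.** Suppose all versions have true sensitivity 85%, are scored on the same n reference-positive charts with correlation ρ between versions, and the best is reported. Approximate optimism = m·√(0.85·0.15/n)·√(1−ρ), where m is the expected maximum of K standard normal values (1.539 for K = 10, 0.846 for K = 3). For K = 10, n = 300 and ρ = 0.9 this is 1.539 × 2.06 × 0.316 = 1.0 point. Simulated values for K = 10, in points:

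| n | ρ = 0.9 | ρ = 0.5 |
|---|---|---|
| 150 | +1.4 | +3.1 |
| 300 | +1.0 | +2.2 |
| 500 | +0.8 | +1.7 |

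With K = 3 and n = 300 the optimism falls to about +0.5 (ρ = 0.9) or +1.2 (ρ = 0.5).

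**B. Stop at the first version that reaches a target.** Suppose true sensitivity rises over ten versions (75%, 77%, ..., 93%) and the assumed target is 85%. For fresh batches, let c be 0.85n rounded up and X_j the number of charts correctly classified by version j, whose true sensitivity is s_j. The chance of stopping at version j is w_j = P(X_j ≥ c) × the product over earlier versions of P(X_i < c). The optimism is Σ w_j·(E[X_j/n | X_j ≥ c] − s_j) / Σ w_j. The fresh-batch row is exact binomial; the same-chart row is simulated at ρ = 0.9.

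| | n = 100 | n = 150 | n = 300 |
|---|---|---|---|
| Fresh batch each time, passing batch reported | +3.8 | +2.7 | +1.6 |
| Same charts reused | +1.3 | +0.9 | +0.5 |

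Targets of 80% and 90% give +1.2 to +3.8 (fresh) and +0.5 to +1.6 (same charts). With fresh batches and the 85% target, the version that passes is truly below target in 54%, 36.5% and 24% of runs.

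**C. Price of reserving charts.** Take 300 reference-positive charts and sensitivity 85%. The half-width of the 95% interval is 1.96·√(0.85·0.15/n): ±4.0 points on all 300, ±5.7 on a reserved 150, ±7.0 on a reserved 100. Root-mean-square error is 2.9 (half) or 3.6 (third). Unsplit, for the best of ten versions, it is 2.2 (ρ = 0.9) or 2.7 (ρ = 0.5). The nominal 95% interval on the unsplit figure covers about 94% at ρ = 0.9 and 89% at ρ = 0.5.

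**D. Sampling frame.** If every reviewed chart meets the base definition, false negatives and true negatives are both zero by construction. Apparent sensitivity is TP/(TP + 0) = 100% and apparent specificity is 0/(0 + FP) = 0%, so neither is informative. PPV = TP/(TP + FP) can be estimated, and narrower variants can be compared with one another.

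PPV does not fix sensitivity. With an assumed 2,500 definition-positive encounters at PPV 85%, TP = 2,125. If 1%, 3% or 5% of an assumed 17,500 definition-negative encounters have CAP, sensitivity is 2125/2300 = 92%, 2125/2650 = 80% or 2125/3000 = 71%.

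The two-drug sample overlaps the antibiotic criterion but leaves the ICD-10 and imaging elements free to vary, so it can contain definition-negative charts. CAP patients treated without either drug are outside it.

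**The case against.** The case for leaving the plan alone has weight.

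- Study Design calls the Aim 1 measures purely descriptive. That excuses the absence of a formal test, though a descriptive accuracy estimate can still be optimistic.
- The indicators are short rules based on national guidelines, not a fitted model. Iteration may largely mean correcting record extraction, with few and very similar versions. In that case the optimism is near the low end, and reserving charts buys little. This stands.
- Total error is not reduced in any split worked in C. This also stands; the gain is only an unbiased figure with honest coverage.
- The two-drug random sample can supply sensitivity and specificity. It can, for recipients of those drugs.

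A reader might also infer more than the text supports:

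- *That tuning charts will be reused.* The plan does not say so.
- *That the CAP definition is iterated until it passes.* The iteration sentence covers the indicators only; the CAP definition is refined and then validated.
- *That the main CAP validation has no chart source at all.* Criteria are assessed within the cohort, and a different population is named only for the secondary component. The listed cohort is the natural reading, although the plan does not say so outright.
- *That a missing numeric target, freeze date or chart allocation is an error.* These are details that would be useful to add. Aims 2 and 3 already place validation before use.
- *That Aim 3 is biased.* Optimistic accuracy figures do not reclassify any encounter in either period, so they do not by themselves bias the pre-post contrast.

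**Conclusion.** The point holds in limited form and is of low severity. As written, the indicator accuracy figures would be selected for passing and would tend to overstate performance by roughly 0.5 to 4 points. That range rests on assumed sensitivity, chart numbers, number of versions, correlation and target. It sits at the low end if versions are few or alike, and at the high end with small fresh batches.

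The frame point needs no assumed figures. Charts chosen by the CAP definition's own elements cannot give that definition's sensitivity or specificity, and the only described sample that can does so for azithromycin/doxycycline recipients. It does not touch the indicators, because the CAP cohort can contain both appropriate and inappropriate prescribing.

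**What to change.** Within the planned maximum of 1500 charts:

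1. Once the choice and duration indicators are final, report their sensitivity and specificity on a last random batch of charts used neither for tuning nor for deciding when to stop. Report that result whatever it is.
2. Report PPV for definition-positive charts. State the sensitivity and specificity of the CAP definition as applying to azithromycin/doxycycline recipients only. A wider claim would need definition-negative charts sampled from a broader frame and weighted by the inverse of the sampling fraction.

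It would also help to state what level counts as acceptable, when the definitions are frozen, which charts serve each component, and whether any are reused.

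The cost of item 1 is precision: for example ±5.7 rather than ±4.0 points if half of 300 reference-positive charts are reserved at an assumed 85% sensitivity, with no reduction in total error. Item 2 needs no extra charts if the claim is restricted as described.

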**Aim 2:**

We will then generate reports of appropriate antibiotic choice and duration using the indicators validated in Aim 1. Through a user-centered design process, we will optimize the structure and delivery of these feedback reports through conducting interviews with a small number of clinical provider stakeholders. We will also perform surveys of all clinicians during the intervention focused on feasibility and acceptability of the intervention.

**Aim 3:**

We will conduct a quasi-experimental study in the adult inpatient settings measuring the impact of implementing the feedback reports on appropriateness of antibiotic choice and duration for CAP using the validated indicators. The baseline, pre-intervention period will last approximately up to 24 months and the intervention period will last up to 24 months.

**Secondary aim:**

We will use the retrospective cohort from aim 1 to assess racial disparities in antibiotic prescribing for CAP. Briefly, we will use the two measures of antibiotic prescribing appropriateness to assess for differences in appropriate prescribing by race, adjusting for other variables.

**Study sites:**Adult

The Hospital of the University of Pennsylvania (HUP) is a 774-bed academic quaternary acute care medical center. There are over 36,000 admissions, 1,500,000 outpatient visits, and 65,000 Emergency Department visits annually.

Penn Presbyterian Medical Center (PPMC) is a 324-bed urban community acute care hospital in West Philadelphia. There are 12,000 admissions, 130,000 outpatient visits, and 31,000 ED visits annually.

Chester County Hospital (CCH) is a 257-bed facility with 13,521 admissions, 425,107 outpatient visits, and 45,317 ED visits annually. The service area is primarily urban and suburban Chester County, Pennsylvania.

**Study subjects:**

There are two study populations for this study: patients and clinicians.

Patients with community acquired pneumoniaInclusion:

1. Diagnosis of community acquired pneumonia based on ICD-10 diagnostic codes (see appendix 1)
2. Prescribed one or more antibiotic within the first 48 hours of hospitalization AND at least one dose administered between 24 and 48 hours OR discharged within 48 hours on antibiotics
3. Chest x-ray or chest CT within 48 hours of admission

Exclusion

1. Transfer from another healthcare facility
2. Died within the first 48 hours of admission

For the secondary component of Aim 1 in which we compare the electronic definition of CAP and provider selected indication with manual chart review, our eligible patient population will include all adult patients who received at least one dose of doxycycline or azithromycin within the first 48 hours of admission. Patients who die within the first 48 hours of admission will be excluded. A random sample will then be selected for chart review.

Our interaction with patients will be limited to review of existing EHR data. We will have no direct contact with patients. Appropriateness of antibiotic use will be reported on an encounter level; data will be aggregated prior to giving feedback to clinicians, though, clinicians may be provided with information on prescribing only for patients for whom they prescribed (or supervised the prescribing of) antibiotics.

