#### **Intervention design and implementation:**

The intervention will consist primarily of an automated prescribing feedback report delivered in aggregate to clinicians. The precise content of the report will be developed with stakeholder feedback, but we anticipate these reports will include such data as: 1) number of patients seen by the prescriber group with the target condition; 2) proportion of patients for which the choice of antibiotic was correct (based on electronic indicators); 3) proportion of patients for which duration of prescribing was correct; and 4) proportion of patients for which both indicators were correct. Clinicians may be provided with patient-level information on prescribing only for patients for whom they prescribed (or supervised the prescribing of) antibiotics.

We will work with our sponsor (the CDC) and key stakeholder champions to engage in a rapid user centered design process to create feedback reports that will fit the prescribing context. In previous work we have found this contributes to greater levels of acceptance by clinicians. First, we will optimize the form of the report (how information is displayed) and how the reports will be delivered to prescribers (e.g. individually via email, embedded in a dashboard, provided verbally and division quality improvement meetings). Second, we will determine appropriate implementation supports that will be needed to accompany the introduction of the feedback reports to each clinical setting. Potential implementation supports will include educational materials for prescribers, communication about the feedback reports to bolster prescriber understanding and trust, and champion-led meetings to ensure that prescribers are aware of the intervention. These activities will be designed with scalability in mind, and so they may be used across diverse settings without negatively impacting operations. Clinician champions will be engaged to inform this intervention as part of the study team, and providers will also be recruited as research subjects to participate in the design process.

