**Outcomes:**

For aim 1, we will assess sensitivity and specificity of the electronic definition of CAP and the antibiotic prescribing indicators.

In order to demonstrate the effect of the intervention (aims 2 and 3), we will track appropriateness of antibiotic use based on the key indicators in the automated reports for the selected targeted conditions prior to and following implementation of the stewardship interventions. The following indicators will be assessed:

- 1) Choice of antibiotic therapy: administration of a first-line agent within 48 hours of admission
- 2) Duration of therapy: all antibiotic durations  $\leq$  5 days are classified as appropriate

The primary outcome in this study is appropriate antibiotic use for CAP at the encounter level. If an encounter is associated with appropriate antibiotic use for both metrics, the encounter will be classified in the numerator as “appropriate” antibiotic use. The denominator will consist of all CAP encounters. As a secondary analysis, we will separately analyze appropriate antibiotic choice for CAP and appropriate antibiotic duration for CAP. Additional secondary outcomes include: hospital readmission within 30 days from the index visit, ED or primary care revisit within 30 days of the index visit with a new antibiotic prescription for a different antibiotic.

Finally, we will assess implementation metrics, including provider engagement with the feedback reports, as well as provider responses to interviews and surveys conducted as part of the assessment of feasibility and acceptability of the intervention.

Secondary aim: The same two outcomes of appropriateness (choice of antibiotic therapy and duration of therapy) will be used for this aim.

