**Analysis:**

At the level of the encounter, patient-specific variables will be compared in the baseline and intervention periods using chi-squared or Wilcoxon rank-sum testing as appropriate. For the primary analysis, a multivariate logistic regression model will be performed at the encounter level, with the intervention (i.e., baseline period vs intervention period) as the primary binary exposure of interest. Calendar month will be included separately in the model, allowing for adjustment for seasonal variation in antibiotic prescribing. We will additionally analyze these data as a pre-post study with segmented regression analysis. This would allow us to assess the immediate change in the outcomes of interest (i.e., appropriate antibiotic use, reflecting antibiotic choice and antibiotic duration) as well as the slope of change occurring associated with the implementation of the intervention. In this analysis we would also control for potential confounders such as changes in the patient population, census, admissions, nurse staffing, etc.

Secondary aim: At the level of the encounter, differences in proportion of appropriate prescribing will be compared by race, using chi-squared testing. Then multivariate logistic regression will be performed at the encounter level, with race as the primary exposure of interest, incorporating other potential confounders in the model.

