## Appendix 1. Diagnostic codes used to define Community Acquired Pneumonia (CAP)

ICD-10 Code	Code Description
J09.X1	INFLUENZA WITH PNEUMONIA
J10.00	INFLUENZA DUE TO OTHER IDENTIFIED INFLUENZA VIRUS WITH PNEUMONIA
J10.01	INFLUENZA DUE TO OTHER IDENTIFIED INFLUENZA VIRUS WITH THE SAME OTHER IDENTIFIED INFLUENZA VIRUS PNEUMONIA
J10.08	INFLUENZA DUE TO OTHER IDENTIFIED INFLUENZA VIRUS WITH OTHER SPECIFIED PNEUMONIA
J11.00	INFLUENZA DUE TO UNIDENTIFIED INFLUENZA VIRUS WITH UNSPECIFIED TYPE OF PNEUMONIA
J11.08	INFLUENZA DUE TO UNIDENTIFIED INFLUENZA VIRUS WITH SPECIFIED PNEUMONIA
J12.0	PNEUMONIA DUE TO ADENOVIRUS
J12.1	PNEUMONIA DUE TO RSV
J12.2	PNEUMONIA DUE TO PARAINFLUENZA VIRUS
J12.3	METAPNEUMOVIRUS PNEUMONIA
J12.8	OTHER VIRAL PNEUMONIA
J12.81	PNEUMONIA DUE TO SARS-ASSOCIATED CORONAVIRUS
J12.82	PNEUMONIA DUE TO CORONAVIRUS DISEASE 2019
J12.89	OTHER VIRAL PNEUMONIA
J12.9	VIRAL PNEUMONIA, UNSPECIFIED
J13	PNEUMONIA DUE TO STREPTOCOCCUS PNEUMONIAE
J14	PNEUMONIA DUE TO HEMOPHILUS INFLUENZAE
J15	PNEUMONIA DUE TO KLEBSIELLA PNEUMONIAE
J15.1	PNEUMONIA DUE TO PSEUDOMONAS
J15.2	PNEUMONIA DUE TO STAPHYLOCOCCUS, UNSPECIFIED
J15.21	PNEUMONIA DUE TO STAPHYLOCOCCUS AUREUS
J15.211	PNEUMONIA DUE TO METHICILLIN SUSCEPTIBLE STAPHYLOCOCCUS AUREUS
J15.212	PNEUMONIA DUE TO METHICILLIN RESISTANT STAPHYLOCOCCUS AUREUS
J15.29	PNEUMONIA DUE TO OTHER STAPHYLOCOCCUS
J15.3	PNEUMONIA DUE TO STREPTOCOCCUS, GROUP B
J15.4	PNEUMONIA DUE TO OTHER STREPTOCOCCI
J15.5	PNEUMONIA DUE TO ESCHERICHIA COLI
J15.6	PNEUMONIA DUE TO OTHER GRAM-NEGATIVE BACTERIA
J15.7	PNEUMONIA DUE TO MYCOPLASMA PNEUMONIAE
J15.8	PNEUMONIA DUE TO OTHER SPECIFIED BACTERIA
J15.9	UNSPECIFIED BACTERIAL PNEUMONIA
J16.0	CHLAMYDIAL PNEUMONIA
J16.8	PNEUMONIA DUE TO OTHER SPECIFIED INFECTIOUS ORGANISMS
J17	PNEUMONIA IN DISEASES CLASSIFIED ELSEWHERE
J18.0	BRONCHOPNEUMONIA, UNSPECIFIED ORGANISM
J18.1	LOBAR PNEUMONIA, UNSPECIFIED ORGANISM
J18.8	OTHER PNEUMONIA, UNSPECIFIED ORGANISM
J18.9	PNEUMONIA, UNSPECIFIED ORGANISM
A37.01	WHOOPING COUGH DUE TO BORDETELLA PERTUSSIS WITH PNEUMONIA

A37.11	WHOOPING COUGH DUE TO BORDETELLA PARAPERTUSSIS WITH PNEUMONIA
A37.81	WHOOPING COUGH DUE TO OTHER BORDETELLA SPECIES WITH PNEUMONIA
A37.91	WHOOPING COUGH, UNSPECIFIED SPECIES WITH PNEUMONIA
A48.1	LEGIONNAIRES' DISEASE
J22	UNSPECIFIED ACUTE LOWER RESPIRATORY INFECTION

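### The 24–48 hour antibiotic condition for entry drops courses stopped before 24 hours, so feedback on duration can change who enters the primary denominator

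*Combined protocol and SAP*

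**What the plan says.** Under Study subjects, criterion 2 for patients has two parts: "Prescribed one or more antibiotic within the first 48 hours of hospitalization", and then "at least one dose administered between 24 and 48 hours OR discharged within 48 hours on antibiotics". The parts are joined by AND and OR without brackets.

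Under Outcomes, the primary outcome is an encounter that passes both indicators, and "The denominator will consist of all CAP encounters". The choice indicator is "administration of a first-line agent within 48 hours of admission". Under the duration indicator, all courses of up to "5 days are classified as appropriate", with no minimum.

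Under Intervention design and implementation, the anticipated report content includes the "proportion of patients for which duration of prescribing was correct". Under Analysis, the primary model is an encounter-level logistic regression "with the intervention (i.e., baseline period vs intervention period) as the primary binary exposure of interest", with calendar month as a covariate. A segmented regression is added, with control for patient mix, census, admissions and staffing.

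Appendix 1 admits viral codes, for example "VIRAL PNEUMONIA, UNSPECIFIED".

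**The concern.** Whether an encounter is counted depends partly on a prescribing decision made after admission, and the feedback reports bear on the same kind of decision. A patient with a qualifying code, qualifying imaging and antibiotics started on arrival is counted if a dose is given after 24 hours. If treatment stops before then and the patient does not leave within 48 hours on antibiotics, the same patient is not counted, although the course is among the shortest and would pass the duration indicator.

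If such early stops become more frequent in the intervention period, they leave both numerator and denominator. The two periods then compare differently selected encounters. Covariate adjustment cannot restore encounters that never enter the data set, and the segmented regression uses the same selected set. Viral codes make the route plausible, since antibiotics may be started and then withdrawn in such patients.

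**Working it through.** **The plan's own figure.** The Sample size section gives 776 in total for 50% versus 60%. Alpha, power and allocation are not stated. Assuming two-sided 5%, 80% power, equal periods, pooled variance and no continuity correction:

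n per period = [1.96 × √(2 × 0.55 × 0.45) + 0.842 × √(0.5 × 0.5 + 0.6 × 0.4)]² / 0.10² = [1.379 + 0.589]² / 0.01 ≈ 387.4, so 388, and 2 × 388 = 776. The figure reproduces and is not in dispute.

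**Who is lost.** Let A = antibiotic prescribed within 48 h, B = a dose at 24–48 h, C = discharged within 48 h on antibiotics. With B and C both false, A AND (B OR C) is false, and so is (A AND B) OR C. The early-stopped encounter is excluded under either grouping. With A and B true, the encounter is included under either grouping, so a course stopped after a dose at 24–48 h stays in.

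**Inputs for the size.**
- Baseline rate 50% (Sample size).
- f = extra share of encounters stopped before 24 h in the intervention period and so dropped. The documents do not give it; assumed range 1% to 10%.
- a = share of those dropped that would otherwise have been appropriate. Not given; range 0 to 1.
- Those stopped early received a first-line agent, so each would pass both indicators if counted. This is an assumption, relaxed below.
- The remaining encounters are unchanged. Early stops that already occur at baseline are set aside.

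**Formulas.** Measured rate = (0.5 − f·a)/(1 − f). Rate with the dropped encounters added back = 0.5 − f·a + f. The gap between them simplifies to f × (1 − measured rate).

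| f | a | Measured | Added back | Gap (points) |
|---|---|---|---|---|
| 1% | 0 | 50.5% | 51.0% | 0.5 |
| 1% | 1 | 49.5% | 50.0% | 0.5 |
| 2% | 0 | 51.0% | 52.0% | 1.0 |
| 2% | 1 | 49.0% | 50.0% | 1.0 |
| 5% | 0 | 52.6% | 55.0% | 2.4 |
| 5% | 0.5 | 50.0% | 52.5% | 2.5 |
| 5% | 1 | 47.4% | 50.0% | 2.6 |
| 10% | 0 | 55.6% | 60.0% | 4.4 |
| 10% | 0.5 | 50.0% | 55.0% | 5.0 |
| 10% | 1 | 44.4% | 50.0% | 5.6 |

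Per 1,000 encounters at f = 5%, a = 0: 500/950 = 52.6% measured, and (500 + 50)/1,000 = 55.0% with the 50 added back.

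**Without a first-line agent.** These encounters fail the composite whatever their duration, so a = 0 and the added-back rate stays at 50.0%. At f = 5% the measured rate is 500/950 = 52.6%, which is 2.6 points too high.

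**Against the precision available.** The plan expects up to 10,000 encounters. If they split evenly, the standard error of the difference is √(2 × 0.25/5,000) = 1.0 point, and about 2.8 points is detectable at 80% power. A rise from 50.0% to 52.6% by deletion alone would reach two-sided 5% significance about 74% of the time; at f = 1% the chance is about 7%, and at 2% about 17%.

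**The case against.** The strongest reply is that the condition serves the case definition. Aim 1 seeks to identify patients actually being treated for community acquired pneumonia, and requiring continued treatment plausibly screens out empirical starts in whom pneumonia was soon ruled out. Because the duration rule has no lower limit, scoring all of those as appropriate could inflate the rate. This stands, and it is a reason to keep the present definition for the primary analysis. Aim 1 also plans to examine inclusion and exclusion criteria, but only for sensitivity and specificity, so it would not show a difference in exclusions between periods.

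Three stronger readings are tempting, and the documents do not support them.

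- A reader might infer that every early stop is lost. A patient treated to 36 hours, with a dose after 24 hours, and discharged without antibiotics is included. Courses stopped later but within 5 days, where a 5-day threshold has most room to act, also stay in.
- A reader might infer that the intervention does change the denominator. No early-stop rate is given, and nothing shows that the reports would move it. Stopping before 24 hours earns no more credit than stopping at day 5, so the shift may be small.
- A reader might infer a bias against the intervention. The measured rate falls below the added-back rate only if those stopped early received a first-line agent. Even then, deletion alone can move it above or below the 50% baseline.

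**Conclusion.** The structural point holds: eligibility depends on prescribing after admission, the feedback bears on that prescribing, and the plan neither counts the excluded encounters by period nor tests their effect. It is a possibility of unknown size, not a demonstrated bias.

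On the assumptions above, with a first-line agent given, the understatement is about 0.5–1 point for an extra 1–2% lost, 2.4–2.6 points for 5% and 4.4–5.6 points for 10%. Against the 50% baseline, a 5% loss alone can put the observed rate anywhere from 47.4% to 52.6%. A loss of 1–2% would matter little beside a planned 10-point effect. A loss of 5% or more would matter for a smaller observed effect, and a larger sample would not remove it. This is a cheap improvement to the plan and does not invalidate the design.

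**What to change.** 1. Keep the Study subjects definition for the primary analysis, and write criterion 2 with explicit AND/OR grouping.
2. Report, by period and by month, the number of encounters that meet every other criterion and fail only the 24–48 hour/discharge condition.
3. Prespecify a sensitivity analysis that repeats the primary model with those encounters added back, scored by the existing choice and duration indicators.
4. State in advance that the primary result will be interpreted with caution if the excluded fraction differs between periods or the two analyses disagree.

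Two variants should be avoided. Requiring a dose in the first 24 hours would drop patients first dosed at 24–48 hours, who are eligible now. Switching the conclusion automatically to the wider set would move it from the definition validated in Aim 1 to an unvalidated one, and a change in the mix of viral cases could trigger the switch without any effect of the intervention.

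The cost is one more pull from the same data warehouse, one table and one repeated model. The downside is that the added set will include some patients in whom pneumonia was ruled out early, whose short courses would count as appropriate in duration. That is why it is a sensitivity analysis and not a replacement.
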